12.5. Safety Analysis

The disposition of the patients will be summarized by tabulating the number of screened, randomized, completed, and discontinued patients. The reasons for premature discontinuations will be tabulated.

The extent of exposure to study treatment will be summarized for each dose level. For the patients who received CVT-301 treatment in the CVT-301-004 study, the total exposure will be the sum of exposure in the CVT-301-004 study and the CVT-301-004E study.

All AEs will be coded using the Medical Dictionary for Regulatory Activities (MedDRA) dictionary. The TEAEs (i.e., events which start or worsen during the study treatment) will be tabulated by treatment group, system organ class, and preferred term. Both patient and event counts will be calculated. In addition, the TEAEs will be evaluated by seriousness, severity, and causality to the study treatment. The AEs leading to a premature discontinuation or dose adjustment will also be summarized. The AEs will be summarized by dose level (CVT-301 DL1 or CVT-301 DL2). Descriptive statistics will be used to describe the overall incidence of TEAE normalized for duration of exposure (number of TEAEs divided by the total exposure to CVT-301 measured as patient years). Furthermore, the time of onset of the TEAEs will be summarized.

For vital signs, ECG parameters, spirometry, the changes from pre-dose to post-dose assessments of the corresponding day will be calculated and compared between the treatment groups using descriptive statistics. For spirometry and safety laboratory variables, the differences in pre-dose values between study days will be described. Furthermore, the changes in the spirometry values and difference between the groups (DL1/DL2 or patients treated with CVT-301/placebo in CVT-301-004) will be estimated using a Mixed Model for Repeated Measurements (MMRM) similar to the one used for the efficacy variables. The proportions of patients meeting ATS quality criteria (and also for those ‘rejected’) will be summarized. Changes from baseline to follow-up in the rating scales for assessing suicidality, somnolence, and impulse control disorders will be summarized descriptively.

At least the following variables will be analyzed:

- Vital signs: standard and orthostatic systolic and diastolic BP and HR.

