## Statistical Analysis Plan

- For the primary analysis of spirometry and selected efficacy endpoints, likelihood-based modeling approach will be used to handle incomplete data. For this purpose, Mixed Model for Repeated Measures (MMRM) will be applied (see [Section 8.1.](#))
- Sensitivity analysis for spirometry and selected explorative efficacy endpoints will be conducted using the Multiple Imputation (MI) approach, i.e. by replacing each missing value with a set of plausible values that represent the uncertainty about the right value to impute, see [Section 9.1.](#)
- For the binary explorative efficacy endpoints, sensitivity analyses will be conducted using worst case imputation, where visits with missing data are counted as non-resolved (primary method), see [Section 8.1.](#)
- For AEs, the overall incidence of TEAEs, normalized for duration of exposure will be calculated to account for the shorter follow-up time in patients who discontinue the study prematurely, see [Section 9.4.](#)

The Safety and ITT population will be used for the analysis of the primary and secondary endpoints. This population includes all patients enrolled to study CVT-301-004E who received at least 1 dose of inhaled CVT-301, regardless of whether they have post-baseline data or not for the variable in question. The patients with no post-baseline data will not contribute to the analyses performed with the MMRM approach, but they do contribute to the sensitivity analyses using the MI approach. Due to this, no additional population, like a modified ITT population including only the patients with post-baseline will be defined.

Safety data (other than the primary endpoint) will not be subjected to any imputation and will be summarized on an observed case basis.

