### 9.2. EXTENT OF EXPOSURE

The following information will be summarized by treatment group and overall:

- The number of patients with dose change
- Duration of exposure to CVT-301 inhalations (days)
- Total exposure to CVT-301 inhalation, expressed as person years (sum of exposure to CVT-301 inhalations over all patients, classified by treatment group)
- Total number of doses and capsules taken, by visit and overall. Average number of daily doses and number of capsules, by visit and overall
- Proportion of days with 5, 4, 3, 2, 1 or 0 doses administered
- Proportion of patients using 5, 4, 3, 2, 1 or 0 doses/day at least once

In addition, these in-clinic data will be summarized by treatment group and visit:

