### 9.4. ADVERSE EVENTS

All AEs will be coded using the MedDRA version 17.0.

Treatment-emergent adverse events (TEAEs) are defined as all AEs that start after the patient receives the first dose of CVT-301 after the relevant baseline (see Section 6.2 for the definition of baseline). Events will be classified as drug-related if the AE is classified as possibly, probably, or definitely related to study drug.

Events with a missing start time, but with a start date equal to the date of first dose of study drug will be considered treatment-emergent. If the AE start date is incomplete, then it will be imputed as follows for the purpose of determining TEAE:

- If the start date is completely missing, the start date will be equal to the first dose date. However, if the stop date is not missing and is before the first dose date, then the stop date will be used instead.

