## Statistical Analysis Plan

- If the start day is missing, the first day of the month will be used.
- If the start day and month are missing, then the first day of the first month (January) will be used.

The original date and time will be shown on all listings of AEs. Listings will be provided for all AEs, serious AEs, AEs leading to study drug discontinuation, AEs leading to dose reduction, and deaths.

TEAEs will be summarized by SOC and PT for each treatment group and CVT-301 overall. TEAEs with onset after the treatment period are attributed to the treatment group during the treatment period. Both event and patient counts, where applicable, will be summarized. The counts will be complemented by percentages will be calculated for the patient counts unless otherwise specified. In addition, the incidence of TEAEs, normalized for duration of exposure to CVT-301 will be presented (number of TEAEs divided by the total exposure to CVT-301, measured as patient years).

- An overall summary of the number and percentage of patients reporting TEAEs and the number of TEAE events, drug-related TEAEs, severe TEAEs, serious TEAEs, TEAEs leading to dose interruption, TEAEs leading to study drug discontinuation, TEAEs leading to dose reduction and TEAEs leading to death
- TEAEs by SOC and PT, both as event and patient counts
- TEAEs by PT, both as event and patient counts
- Drug-related TEAEs by SOC and PT, both as event and patient counts
- Severe TEAEs by SOC and PT, both as event and patient counts
- Drug-related TEAEs by SOC, PT and severity, as event counts; percentages will be calculated for the event count out of total number of events
- Drug-related TEAEs by SOC, PT and relationship, as event counts; percentages will be calculated for the event count out of total number of events
- Serious TEAEs by SOC and PT, both as event and patient counts
- TEAEs leading to study drug interruption, both as event and patient counts
- TEAEs leading to study drug withdrawal, both as event and patient counts
- TEAEs leading to dose reduction, both as event and patient counts
- Most common AEs, both as event and patient counts, most common TEAEs is defined any AE preferred term occurred in greater than 10% total patients
- Time to first onset of most common AEs, classified as 0-1 months, >1-3 months, >3-6 months, >6-9 months and after 9 months, where the date of TEAE onset will be used as the time point for classification

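### The exposure-normalised TEAE rate counts post-treatment events but no post-treatment time, and exposure duration itself is not defined

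*SAP*

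**What the plan says.** **Numerator.** SAP 9.4 has TEAEs "defined as all AEs that start after the patient receives the first dose of CVT-301 after the relevant baseline". It gives no cut-off after last dose and no exception for the drug holiday. It adds that "TEAEs with onset after the treatment period are attributed to the treatment group during the treatment period".

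**Denominator.** The rate in SAP 9.4 is the "number of TEAEs divided by the total exposure to CVT-301, measured as patient years". SAP 9.2 describes total exposure as the "sum of exposure to CVT-301 inhalations over all patients, classified by treatment group" and lists duration in days, but gives no rule for deriving it.

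**Purpose.** SAP 6.3 presents the rate as the way "to account for the shorter follow-up time in patients who discontinue the study prematurely". It is tabulated by system organ class and preferred term, by dose and by study of origin (Tables 14.3.2.2.5 and 14.3.2.2.6).

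**Off-drug collection.** Protocol 10.1.4, 10.1.4.1 and Appendix 10 schedule adverse-event enquiries at a day-14 call (holiday, or after TV6 or early withdrawal), at a day-28 call (after TV6 or early withdrawal), and at the re-supply visit that ends the holiday. Protocol 11.1.9 requires SAEs to be reported up to 4 weeks after stopping.

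**Protocol definition.** Protocol 12.5 is narrower: "The TEAEs (i.e., events which start or worsen during the study treatment". The SAP prevails where the two differ (Protocol 12, SAP 2), and SAP 11 does not list this difference.

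**The concern.** An events-per-person-year rate is interpretable only if every event counted could have arisen in the time counted. Here the weeks after last dose can contribute events but not time. The post-treatment window is about the same length for everyone, so its proportional effect is largest where exposure was short. Those are the early withdrawals for whom SAP 6.3 introduces the rate. This is a safety study, and the rate is one of its main descriptive summaries of adverse events.

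The undefined duration leaves two more off-drug windows unsettled. One is the 28-day holiday. The other is the 1–14-day interval (longer with sponsor approval) before TV1 for patients who had active drug in CVT-301-004. Their baseline, and so their TEAE window, starts in that earlier study. Protocol 12.5 adds the two studies' exposures without mentioning the interval.

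**Working it through.** Neither document states a TEAE rate or a precision target, so there is no planned figure to reproduce.

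**Inputs from the documents**
- 390 enrolled and about 290 completing, so 100 withdraw (SAP 3.5, Protocol 12.1).
- 52 weeks of treatment (SAP 3.8).
- 4 weeks of post-treatment collection (the day-28 call and the SAE window).

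**Assumptions, not in the documents**
- Mean withdrawal at Week 8, 16 or 26.
- Off-drug to on-drug event-rate ratio r of 1, 0.5 or 0.25.
- All 390 patients have the 4 weeks of collection.
- No holiday.

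**Formulas**
- SAP rate = (E_on + E_off) / T_on.
- Matched on-drug rate = E_on / T_on. The SAP rate exceeds it by the fraction r × T_off / T_on.
- Matched whole-observation rate = (E_on + E_off) / (T_on + T_off). The SAP rate exceeds it by T_off / T_on, whatever r is.

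Both excesses are positive whenever off-drug events occur, so the direction does not depend on the assumptions.

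**Pooled rate.** T_off = 390 × 4 = 1,560 patient-weeks.

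| Mean withdrawal | T_on (patient-weeks) | r = 1 | r = 0.5 | r = 0.25 |
|---|---|---|---|---|
| Week 8 | 290×52 + 100×8 = 15,880 | 9.8% | 4.9% | 2.5% |
| Week 16 | 290×52 + 100×16 = 16,680 | 9.4% | 4.7% | 2.3% |
| Week 26 | 290×52 + 100×26 = 17,680 | 8.8% | 4.4% | 2.2% |

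The columns give the excess over the on-drug rate. The r = 1 column is also the excess over the whole-observation rate for any r.

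**One patient's contribution at r = 1.** Stopping at Week 4: 4/4 = 100%. Stopping at Week 12: 4/12 = 33%. Completing 52 weeks: 4/52 = 7.7%.

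**Between doses.** Take 195 per arm (390/2, assumed), with 35 versus 65 withdrawals at mean Week 16 and r = 1. T_off = 195 × 4 = 780 in each arm.
- 35 withdrawals: T_on = 160×52 + 35×16 = 8,880, so the factor is 1 + 780/8,880 = 1.088.
- 65 withdrawals: T_on = 130×52 + 65×16 = 7,800, so the factor is 1 + 780/7,800 = 1.100.
- Spurious rate ratio: 1.100/1.088 = 1.01.

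**Between study groups (completers, r = 1).** An active rollover with 12 further weeks from CVT-301-004 has 4/64 = 6.3%, against 4/52 = 7.7% for a naïve patient. The ratio is 1.077/1.063 = 1.01.

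**The case against.** Four points against the concern have force.

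- **Unit of reporting.** The SAP reports one pooled rate per group, not a rate for withdrawals. A reader might infer from the single-patient figures that reported rates could double. They could not, because early withdrawals contribute little of the on-drug time (100×8/15,880 = 5.0% to 100×26/17,680 = 14.7%).
- **The holiday.** A reader might infer that holiday events are counted without time. The documents do not establish that. If duration runs from first to last dose, the holiday is already in the denominator. Only patients who reach TV4 or TV5 take it, so it cannot explain any bias from early withdrawal. Patients who took it also have no scheduled adverse-event call after TV6, so a full holiday and a full post-TV6 window should not simply be added together.
- **Length of follow-up.** Collection might be thought to run to the laboratory visit 4 to 5 weeks after TV6, but Appendix 10 schedules no adverse-event enquiry there. Four weeks is what the schedule supports, and not every patient is due the calls, so the r = 1 figures lean high.
- **Comparisons.** The rate is descriptive, and a marked imbalance in withdrawals moves the dose comparison by only about 1%.

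It can also be said that the protocol is itself inconsistent. Its synopsis and section 11.1.8 use open-ended wording close to the SAP's, and the listings keep original onset dates, so off-drug events can be traced. That softens the criticism of the definition. It does not repair the ratio: the SAP's numerator still runs past last dose and its denominator is still exposure.

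**Conclusion.** The defect stands in a modest form. The rate is biased upward against either matched rate, as a direct consequence of the SAP's own wording. The excess over the on-drug rate is about 9–10% at equal on- and off-drug event rates and about 2% at a quarter of the on-drug rate. This rests on the assumed withdrawal times, the assumed rate ratio, and four weeks of collection for everyone. The DL1-versus-DL2 comparison is essentially unaffected, and the documents do not support a claim that groups with more dropout would look materially worse.

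Treatment of the holiday and the between-study gap is undetermined, not shown to be wrong. No inflation figure should be attached to either until exposure duration is defined.

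**What to change.** - **SAP 9.2:** define exposure duration, stating whether the 28-day holiday and the gap between CVT-301-004 and CVT-301-004E are included.
- **SAP 9.4:** use the same window above and below the line, and present two rates: (a) on-drug TEAEs over on-drug person-years; (b) all TEAEs over person-years from first dose to the end of adverse-event collection.
- **SAP 9.4:** tabulate holiday, gap and post-treatment onsets separately. This matters most for the withdrawal terms in the abuse-assessment list. If such events arise only in the 4 weeks off drug but are divided by 52 weeks on drug, the off-drug rate is understated 52/4 = 13-fold.
- **SAP 11:** record that the SAP's TEAE definition departs from Protocol 12.5.

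The cost is SAP wording, one extra rate column and the separate tabulation. Reported on-drug rates will be slightly lower. No new data are needed.

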## Statistical Analysis Plan

### 6. GENERAL ASPECTS FOR STATISTICAL ANALYSIS

#### 6.1. GENERAL METHODS

All patient data will be included in listings. All patients entered into the database will be included in patient data listings. The listings will be generally sorted by the study (and treatment) from which the patient was enrolled, Patient ID (and by visit and by time point, if applicable) within treatment group, unless specified otherwise.

All applicable data will be summarized by treatment group (CVT-301 DL1, CVT-301 DL2, CVT-301 overall) in tables, unless specified otherwise. Furthermore, selected summaries will be broken down into three groups as follows: patients who received CVT-301 in CVT-301-004 study, patients who received placebo in CVT-301-004 study and CVT-301 naïve patients (including CVT-301-005 observational arm patients) (referred to as “treatment/study group” in the SAP). The efficacy data from patients who were enrolled in the CVT-301-003 or CVT-301-009 study will be analyzed separately, as data listings. In addition, a patient disposition table will be provided for CVT-301-003 and CVT-301-009 patients. Where appropriate, data will be summarized by visit and/or time point in addition to treatment group. Unscheduled or repeat assessments will not be included in summary tables, but will be included in listings.

Continuous variables will be summarized using the number of observations (n), mean, SD, median, minimum, and maximum. Standard error of the mean (SEM) will also be provided for summaries of spirometry and efficacy endpoints, if relevant. The same number of decimal places as in the raw data will be presented when reporting minimum and maximum, 1 more decimal place than in the raw data will be presented when reporting mean and median, and 2 more decimal places than in the raw data will be presented when reporting SD and SEM.

Descriptive statistics for categorical/qualitative data will include frequency counts and percentages. The total number of patients in each treatment group/overall (N) will be used as the denominator for percent calculations, unless stated otherwise in the table shell. All percentages will be presented with one decimal point, unless specified otherwise. Percentages equal to 100 will be presented as 100% and percentages will not be presented for zero frequencies.

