## Statistical Analysis Plan

Table 14.3.2.15.1	Treatment-emergent adverse events Leading to Dose Reduction by System Organ Class, Preferred Term and Treatment Group (Safety Population)
Table 14.3.2.15.2	Treatment-emergent adverse events Leading to Dose Reduction by System Organ Class, Preferred Term and Treatment/Study (ITT Population)
Table 14.3.2.16	Listing of Adverse Events Leading to Dose Reduction(Safety Population)
Table 14.3.2.17.1	Most Common Treatment-Emergent Adverse Events (Preferred Term Occurred in >10% of Over Patients) by System Organ Class, Preferred Term and Treatment Group (Safety Population)
Table 14.3.2.17.2	Most Common Treatment-Emergent Adverse Events (Preferred Term Occurred in >10% of Over Patients) by System Organ Class, Preferred Term and Treatment/Study (ITT Population)
Table 14.3.2.18	Listing of Most Common Treatment-Emergent Adverse Events (Safety Population)
Table 14.3.2.19.1	Time to first Onset of most Common Treatment-Emergent Adverse Events by Treatment Group (Safety Population)
Table 14.3.2.19.2	Time to first Onset of most Common Treatment-Emergent Adverse Events by Treatment/Study (ITT Population)
Table 14.3.4.1	Clinical Laboratory Results: PCS and PCSC Criteria
Table 14.3.4.1.1.1	Summary of Clinical Laboratory Results: Hematology by Treatment Group and Visit (Safety Population)
Table 14.3.4.1.1.2	Summary of Clinical Laboratory Results: Hematology Abnormal Values by Treatment Group and Visit (Safety Population)
Table 14.3.4.1.1.3	Summary of Clinical Laboratory Results: Hematology Abnormal Values - Shift from Baseline by Treatment Group and Visit (Safety Population)
Table 14.3.4.1.1.4	Summary of Clinical Laboratory Results: Hematology PCS Values -Shift from Baseline by Treatment Group and Visit (Safety Population)
Table 14.3.4.1.1.5	Summary of Clinical Laboratory Results: Hematology PCSC Values -Shift from Baseline by Treatment Group and Visit (Safety Population)
Table 14.3.4.1.1.6	Clinical Laboratory Results - Hematology PCS and PCSC Values (Safety Population)
Table 14.3.4.1.2.1	Summary of Clinical Laboratory Results: Chemistry by Treatment Group and Visit (Safety Population)
Table 14.3.4.1.2.2	Summary of Clinical Laboratory Results: Chemistry Abnormal Values by Treatment Group and Visit (Safety Population)
Table 14.3.4.1.2.3	Summary of Clinical Laboratory Results: Chemistry Abnormal Values -Shift from Baseline by Treatment Group and Visit (Safety Population)

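### The adverse-event onset table has unequal, open-ended intervals and no time at risk, so a constant risk would look about 2- to 3-fold higher in later intervals than in Month 1

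*SAP*

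**What the plan says.** SAP Section 9.4 plans a table of time to first onset of the most common adverse events, "classified as 0-1 months, >1-3 months, >3-6 months, >6-9 months and after 9 months". The date of onset decides the interval. The terms covered are limited: "most common TEAEs is defined any AE preferred term occurred in greater than 10% total patients". Section 14 lists the table by dose level (14.3.2.19.1) and by treatment/study group (14.3.2.19.2).

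For treatment-emergent events in general, Section 9.4 says: "Both event and patient counts, where applicable, will be summarized". Section 6.1 sets the default percentage base: "The total number of patients in each treatment group/overall (N) will be used as the denominator for percent calculations", unless a table shell says otherwise. Section 12.2.5.2 gives a different default, namely patients in the analysis set with an observation. Neither default is the number still at risk in an interval.

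The SAP does adjust for exposure elsewhere. Section 6.3 says that "the overall incidence of TEAEs, normalized for duration of exposure will be calculated to account for the shorter follow-up time", and Section 9.4 defines the measure as "number of TEAEs divided by the total exposure to CVT-301, measured as patient years". Tables 14.3.2.2.5 and 14.3.2.2.6 report it over the whole period, not by onset interval. Section 16 lists no figures, so no Kaplan-Meier or cumulative-incidence plot is planned.

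Protocol Section 12.5 requires a summary of the time of onset of treatment-emergent events. This table is the only planned summary that provides one.

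**The concern.** The table exists to show whether common adverse events cluster early or build up over about a year of inhaled treatment. Counts in intervals of different length cannot be compared directly, because a 3-month interval collects more first onsets than a 1-month interval at the same risk. Two further effects work in the opposite direction: patients who have had their first event, and patients who have left, can no longer contribute a first onset. The shape of the table therefore mixes risk with interval width, depletion and attrition.

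The open last interval adds a second difficulty. Its length depends on how long each patient is followed, and that differs between the study groups shown side by side in Table 14.3.2.19.2.

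**Working it through.** **Inputs.** The SAP states no figure for this table, so there is nothing to reproduce. From the documents: the interval limits (SAP 9.4), and 390 enrolled with about 290 completing 12 months (SAP 3.5), an implied attrition of 100/390 = 25.6%. Assumed: a 12-month risk of first onset R of 10% to 30%, constant hazards except where stated, and follow-up ending at Month 12 unless stated.

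**Formula.** With onset hazard λ = −ln(1−R)/12 per month and dropout hazard μ = 0 or −ln(290/390)/12 = 0.0247, the share of all patients with first onset in (a, b] is

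λ/(λ+μ) × [exp(−(λ+μ)a) − exp(−(λ+μ)b)].

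**Width alone.** For a rare event without attrition, the ratios to Month 1 are the widths: 2, 3, 3, and 3 if the last interval ends at Month 12.

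**Worked case: R = 15%, with attrition.** λ = 0.01354, λ+μ = 0.03823, λ/(λ+μ) = 0.354.
- Month 0-1: 0.354 × (1 − 0.9625) = 1.33%.
- >3-6 months: 0.354 × (0.8916 − 0.7950) = 3.42%.
- Ratio: 3.42/1.33 = 2.58, although the hazard never changed.

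**Constant hazard, % of patients (ratio to Month 1).**

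| R | Attrition | 0-1 | >1-3 | >3-6 | >6-9 | >9-12 |
|---|---|---|---|---|---|---|
| 10% | none | 0.87 | 1.73 (1.97) | 2.53 (2.90) | 2.47 (2.82) | 2.40 (2.75) |
| 10% | 25.6% | 0.86 | 1.64 (1.90) | 2.27 (2.63) | 2.05 (2.37) | 1.85 (2.15) |
| 15% | none | 1.35 | 2.64 (1.96) | 3.82 (2.84) | 3.67 (2.73) | 3.52 (2.62) |
| 15% | 25.6% | 1.33 | 2.51 (1.89) | 3.42 (2.58) | 3.05 (2.30) | 2.72 (2.05) |
| 30% | none | 2.93 | 5.60 (1.91) | 7.80 (2.66) | 7.14 (2.44) | 6.53 (2.23) |
| 30% | 25.6% | 2.89 | 5.33 (1.84) | 6.99 (2.42) | 5.94 (2.05) | 5.04 (1.74) |

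The 10% rows mark the edge of the range: they sum to 10.0% and 8.7%, so a term observed at that level by Month 12 would not pass the table's threshold.

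**Early excess.** Hazard per month in Month 1, then 1% per month:
- 2%, no attrition: 1.98, 1.94, 2.84, 2.76, 2.67%.
- 2%, with attrition: 1.96, 1.85, 2.54, 2.29, 2.06%. The true halving does not show.
- 3%, with attrition: 2.92, 1.83, 2.52, 2.27, 2.04%.
- 4%, with attrition: 3.87, 1.81, 2.49, 2.25, 2.02%. In these last two cases Month 1 is the largest interval although it is the narrowest, so the excess is visible.

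**The open interval.** SAP 6.2 and 9.4 start the baseline, and so the treatment-emergent period, at the first CVT-301 dose in CVT-301-004 for patients treated with it there. The SAP does not separately state a time origin for the onset table; I take it to be the same. SAP Section 8 uses Week 12 of CVT-301-004 as Month 3, so these patients have about 3 more months: to about Month 15, against Month 12 for the others on the SAP's Week 52 schedule. Protocol Section 10.1.3.9 places the last treatment visit at 56 or 60 weeks, which lengthens the interval for everyone. SAP 9.4 also attributes events after treatment to the treatment group, so they can fall here. At R = 15%, the last interval holds 3.52% if it ends at Month 12 and 6.91% at Month 15 without attrition, or 2.72% and 5.15% with it. That is close to a twofold gap at identical risk. Using one dropout rate for both groups is a simplification, because former CVT-301-004 patients had to complete that study to enter.

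**Check of the fix.** For R = 15% with attrition and 390 patients, Month 0-1 has 5.2 onsets in 383 person-months and >3-6 months has 13.3 in 986. Both give 1.35 per 100 person-months, as do the other intervals.

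**The case against.** The best defence is that this is a descriptive display with stated limits that match the visits at Months 1, 3, 6 and 9. No test or conclusion rests on it, and it meets the protocol's request for an onset summary. A careful reader can allow for the widths of the closed intervals. That much stands, but such a reader could not allow for attrition, depletion or an open interval of unknown length.

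Several stronger readings are tempting, and the documents do not support them:

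- **A uniform threefold rise after Month 1.** Three is the pure width ratio for the 3-month intervals with a rare event and no attrition, and rare events are not in this table. The >1-3 month interval less than doubles at every risk in the range.
- **A true fall shown as a rise.** With the plan's own attrition, the halved hazard gives a roughly flat table with a bump at >3-6 months. It is masked rather than clearly reversed, and larger early excesses remain visible.
- **A plan that ignores exposure.** Whole-period rates per patient-year are planned by dose level and by study group. The gap is confined to the interval table.
- **No other evidence on timing.** The adverse-event listings show onset dates. This is the only planned summary, not the only information.
- **A known fixed percentage base.** The SAP gives two defaults and defers to table shells that are not in the documents. The point does not depend on this, since any base held constant across intervals gives the same ratios.

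The split by study group makes the longer last interval easier to notice, but it does not make the groups comparable in it.

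**Conclusion.** The point holds as a limited one and is a cheap improvement. As specified, a constant risk would appear about 2- to 3-fold higher in later intervals than in Month 1: about 1.8 to 2.0 for >1-3 months, and for the 3-month intervals before Month 9 about 2.1 to 2.6 with 25.6% attrition or 2.4 to 2.9 without. If follow-up ends at Month 12, the last interval is 1.7 to 2.2 times Month 1 with attrition and 2.2 to 2.8 without; with follow-up to Month 15 and attrition it is 3.2 to 4.1. A modest early excess would be hidden; a threefold one would not. Study groups cannot be compared in the open interval.

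These sizes rest on constant hazards, an assumed 12-month risk of 10% to 30%, and attrition inferred from planned enrolment and completion. The direction of the distortion needs only the interval widths and the absence of time at risk. The primary spirometry analysis is not affected.

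**What to change.** Keep the intervals. For each preferred term, add to each interval the patients at risk at its start (still followed and without a previous onset of that term), the person-months at risk, and first onsets per 100 person-months, in both Table 14.3.2.19.1 and Table 14.3.2.19.2. State the time origin, the end of follow-up, and whether the drug holiday and post-treatment time count as time at risk.

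Split the last interval into >9-12 months and >12 months, rather than cutting it off, so that late onsets are kept and the extra follow-up of former CVT-301-004 active patients is shown separately.

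The cost is modest programming for each preferred term, because time at risk for a first onset differs by term. No new data are needed: the onset and exposure dates are already required for the planned tables.
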